### 10.6.1 Adverse Events

Adverse events are coded using the MedDRA adverse event dictionary. Safety evaluations are based on occurred adverse events, laboratory values, vital signs and appearance of collagen VII antibodies, and RCV. Severities of toxicities is described using the NCI Common Toxicity Criteria (CTC) grades.

Adverse events are grouped into pre-treatment adverse events and treatment-emergent adverse events and are tabulated by preferred terminology and by body system for each study phase. The number of adverse event entries, as well as the number of patients are reported. Analyses include tabulation of adverse event type, relationship to KB103, seriousness, and severity of adverse events according to CTCAE.

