2.2.2 Other

- 1) To evaluate the expression of human collagen VII as determined by immunofluorescence (IF)
- 2) To evaluate the presence of anchoring fibrils as determined by immunoelectron microscopy (IEM) post-administration

3 Overview

The Phase I/II studies were randomized placebo controlled intrasubject comparison of KB103-administered and placebo-administered wounds.

To date, KB103 has been administered to 12 patients enrolled onto 4 versions of the Phase I/II protocol. A summary of the protocols and patients enrolled are presented below.

Phase	Protocol:	SN and Date:	# of pts	Wound size	# of wounds treated	Dose	Dosing days
1	v1.0, 19Apr2018	SN0001, 4/20/2018	2, Pts 01-02 Adults	Up to 10cm ²	2: one KB103, one placebo	1e8 PFU/wound/day	0, 2, 14, 28, 30
Following v1.0, the protocol was amended to increase the frequency and PFU level of the doses, and to administer to patients age 5 and older.							
2a	v2.2, 08Oct2018	SN0008, 10/09/2018	4, Pts 03-06 2 adults, 2 children age 13&14	Up to 20 cm ²	3: two KB103, one placebo	3e8 PFU/wound/day with the option to escalate to 6e8 PFU/wound/day	1, 2, 3, 4, 5, 30, 60, 90
Following 2.2, the protocol was amended to administer KB103 every two to three days to correspond with bandage changes. The potential number of doses increased, and the dose level was set at 2e8 PFU/wound/administration.							
2b	v3.1, 12Mar2019 and v3.2*, 25Jun2019	SN0016, 3/4/2019	5, Pts 07-11 3 adults, 2 children age 14&15	Up to 20 cm ²	3: two KB103, one placebo	2e8 PFU/wound/day	Every 2 to 3 days up to 15 per month
Following 3.2, the protocol was amended to administer KB103 in 2 cycles. The age of inclusion was reduced to 2 years old. Wound areas increase to up to 50cm ² , and with the increase in area the dose was increased to 6e8 PFU per area.							
2c	v4.0, 01Aug2019	SN0024, 8/5/2019	3, TBD	Up to 50 cm ²	Up to 3; 2 KB103 and one placebo	6e8 PFU/wound/day	Every 2 to 3 days until wound closure x 2 cycles

*v3.2 clarified the long-term follow-up

4 Study Implementation

Detailed information for the protocol study visits, is provided in the sections below and in the Schedule of Events ([Appendix 1: Schedule of Events](#)).

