9.1 Adverse Events

Verbatim descriptions of AEs will be coded using MedDRA, version to be delineated in the CSR. Summary tables will be provided for all treatment-emergent adverse events (TEAEs), but all AEs will be provided in a listing. A treatment-emergent AE is defined as any AE that newly appeared, increased in frequency, or worsened in severity on or after the initiation of active test article. An AE is considered treatment emergent if the AE start date and time is on or after the start date and time of the first administration treatment dose. If time of the AE is missing and it occurred on the same date as the first administration treatment dose, the AE will be defined as treatment emergent. If the start date of the AE is partial or missing and it cannot be determined if the AE occurred prior to or after the first administration treatment dose, the AE should be defined as treatment emergent.

An overall summary of AEs will include the number of subjects who experienced at least one AE of the following categories: any AE, any TEAE, any drug-related TEAE, any severe TEAE, any serious TEAE, any drug-related SAE, any serious TEAE leading to death, any TEAE leading to premature discontinuation

of treatment, any TEAE leading to premature discontinuation from the study, any TEAE leading to dose interruption of test article, and any serious TEAE leading to premature discontinuation of treatment dose.

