The number and percentage of subjects reporting a TEAE in each treatment group will be tabulated by system organ class and preferred term; by system organ class, preferred term, and severity (mild, moderate, and severe); and by system organ class, preferred term, and relationship (unrelated or related to test article). The incidence of TEAEs will be summarized by preferred term, sorted by decreasing frequency in the KB103 group, for all TEAEs, related TEAEs, serious TEAEs, and TEAEs leading to study drug discontinuation. The number and percentage of subjects reporting a TEAE of wound site reaction (based on the MedDRA higher level term) will be tabulated by treatment group, preferred term and severity (mild, moderate, and severe). The incidence of serious TEAEs, and TEAEs leading to premature discontinuation of treatment by system organ class and preferred term. For all analyses of TEAEs, if the same AE (based on preferred term) is reported for the same subject more than once, the AE is counted only once for that preferred term and at the highest severity and strongest relationship to test article.

In addition, all AEs (including non-TEAEs), serious TEAEs, TEAEs leading to discontinuation of test article, and TEAEs leading to dose interruption of test article will be provided in listings by treatment group, study site, subject, verbatim term, MedDRA system organ class and preferred term, start and end date, seriousness flag, severity, relationship to test article, relationship to study protocol, action taken with test article, non-test article action taken and outcome.

Immune response adverse events due to a severe immune response determined by the Investigator to be possibly, probably or definitely related to KB103 will be summarized by the number and percentage reporting such AEs along with a subject listing.

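### SAP 9.1 plans subject-level adverse event tables only, so the count of AE entries that Protocol 10.6.1 requires appears in no summary table

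*SAP*

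**What the plan says.** Protocol 10.6.1 (Adverse Events) sets the reporting unit for the AE tabulations: "The number of adverse event entries, as well as the number of patients are reported". Both counts are called for.

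SAP 9.1 (Adverse Events) uses one unit. For the overall table: "An overall summary of AEs will include the number of subjects who experienced at least one AE of the following categories". For the main tabulation: "The number and percentage of subjects reporting a TEAE in each treatment group will be tabulated by system organ class and preferred term". The breakdowns by severity and by relationship, and the wound site reaction table, also give the number and percentage of subjects. The remaining TEAE tables are described as incidence. A rule stated to cover all TEAE analyses then says that "if the same AE (based on preferred term) is reported for the same subject more than once, the AE is counted only once". The single count keeps the worst severity and the closest relationship.

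The SAP also plans listings: "Summary tables will be provided for all treatment-emergent adverse events (TEAEs), but all AEs will be provided in a listing". The listing fields include "MedDRA system organ class and preferred term, start and end date, seriousness flag, severity, relationship to test article".

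The SAP section 3 table gives the v4.0 dosing as "Every 2 to 3 days until wound closure x 2 cycles". Protocol sections 5.4, 5.6 and 6 limit each cycle to 3 months.

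**The concern.** The two documents give different rules for the same tables. A programmer who follows SAP 9.1 will produce no count of AE entries anywhere, although the protocol says it is reported. The SAP gives no reason for leaving it out.

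The design gives the omitted count some value. KB103 is applied every few days, and under v4.0 a second cycle begins if the wound re-opens or enlarges. Whether a local reaction occurs once, returns with dosing, or comes back in the second cycle is a reasonable tolerability question, and a subject count cannot answer it. The study is also small: SAP 4.1 gives up to 12 subjects and the protocol synopsis up to 14, so the subject counts are bounded by those totals.

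Read literally, the rule also merges the same preferred term arising at two KB103 wounds of one subject. Two KB103 wounds and one placebo wound is the layout in v2.2 and v3.x and is possible in v4.0.

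**Working it through.** **Step 1. Compare the reporting units.**

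| Output | Subjects | AE entries |
|---|---|---|
| Protocol 10.6.1, AE tabulations | required | required |
| SAP 9.1, overall AE summary | yes | not specified |
| SAP 9.1, by system organ class and preferred term, with severity and relationship | yes | not specified |
| SAP 9.1, incidence by preferred term; serious TEAEs; discontinuations | yes (incidence, count-once rule) | not specified |
| SAP 9.1, wound site reactions | yes | not specified |
| SAP 9.1, listings | individual records | individual records, no total |

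No row of the SAP supplies the second count. Because the count-once rule covers all TEAE analyses, it cannot be recovered from the tables either.

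**Step 2. How much repetition can be hidden.** The documents state no total number of doses, so there is no planned figure to reproduce. I counted from these inputs:

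- interval g = 2 or 3 days (Protocol 5.4 and 5.6);
- cycle length L: 3 months at most, taken as 84 to 92 days (assumption);
- two cycles (Protocol 4.1).

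Doses per cycle = floor((L − 1)/g) + 1, with a dose on Day 1.

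| L (days) | g = 2: per cycle | two cycles | g = 3: per cycle | two cycles |
|---|---|---|---|---|
| 84 | floor(83/2) + 1 = 42 | 84 | floor(83/3) + 1 = 28 | 56 |
| 90 | floor(89/2) + 1 = 45 | 90 | floor(89/3) + 1 = 30 | 60 |
| 92 | floor(91/2) + 1 = 46 | 92 | floor(91/3) + 1 = 31 | 62 |

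Two full cycles therefore allow 56 to 92 scheduled doses per wound area. Protocol 5.7.1 permits a further dose at each of the three monthly visits if a target wound is open, giving at most 59 to 95.

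**Step 3. How far actual numbers may fall below that.** Dosing stops at closure (Protocol 6). Protocol 1.6 reports that chronic but recurring wounds tended to close within 7 to 10 days, though under an earlier schedule of daily doses for 5 days. If the same closure time held under v4.0 (illustration only), a cycle would contain between floor(6/3) + 1 = 3 and floor(9/2) + 1 = 5 doses, or 6 to 10 over two cycles. Wounds open for years stalled and would be dosed for longer.

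**Step 4. Who is affected, and by how much.** The other schedules in SAP section 3 are 5 dosing days (v1.0), 8 (v2.2) and up to 15 per month (v3.x). They cover 2 + 4 + 5 = 11 subjects; 3 are planned under v4.0. A subject with k recorded entries of one preferred term contributes 1 to every SAP table, whatever k is. With the protocol's second count the same subject shows as 1 subject and k entries.

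**The case against.** The case for leaving SAP 9.1 alone has several parts.

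- *Counting once per subject is the normal rule.* This stands. Without it the subject percentages would be wrong. The defect is the missing column beside the subject columns.
- *Recurrence is not lost.* This stands in part. The listings show each recorded event with its dates, severity, relationship and outcome, and with so few subjects they can be read line by line. A reader might infer that a recurring reaction and a single one are reported identically throughout; that is true of the summary tables only. A listing is still not the reported number that Protocol 10.6.1 calls for.
- *Entry counts depend on recording practice.* This stands as a caution. Protocol 9.1.1 prefers a diagnosis to separate symptoms and excludes ordinary disease fluctuation, and off-site events are reported by phone. A persistent reaction may be one entry, so the number of entries is not a clean measure of reactions per dose.
- *No safety decision waits on these tables.* This stands. The stopping criteria in Protocol 5.1 operate through the safety investigation and the monitoring committee, not through the TEAE summaries.

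Two stronger inferences are tempting and should not be drawn.

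The first is a roughly 90-fold understatement of events. That would need a v4.0 subject, dosing every 2 days, no closure in either full cycle and a separate AE entry at every dose. Nothing in the documents suggests such a pattern: Protocol 1.5 and 1.6 report no KB103-related adverse events in the first two subjects or in the four under version 2.

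The second is that the count-once rule contradicts the SAP's own TEAE definition, which covers "any AE that newly appeared, increased in frequency, or worsened in severity on or after the initiation of active test article". The definition decides whether an event qualifies as treatment-emergent; the rule decides how a qualifying event is tabulated. An event that becomes more frequent qualifies, and its subject is counted.

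**Conclusion.** The point holds as a conflict between stated rules. Protocol 10.6.1 requires AE entries and patients; SAP 9.1 delivers patients only and extends the count-once rule to all TEAE analyses. As written, no summary table will contain an event count, and recurrence under repeated dosing is left to the listings.

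The practical size is modest and cannot be fixed in advance, because it depends on how often a term recurs and how it is recorded. The opportunity for recurrence is at most about 56 to 92 scheduled doses over two full v4.0 cycles. This assumes a cycle of 84 to 92 days and an interval of 2 or 3 days, leaves out up to three possible later doses, and applies to 3 planned subjects. The conflict itself needs none of these assumptions.

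**What to change.** In SAP 9.1, restrict the count-once rule to the columns giving the number and percentage of subjects. Add the number of AE entries beside them in the TEAE tables, including the wound site reaction table, so that the output meets Protocol 10.6.1.

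Optionally, give wound site reaction events with the number of administrations as denominator. Protocol 10.6.1 does not ask for this, but it would help fair reading. With two KB103 areas and one placebo area dosed on the same days, there are 2 KB103 administrations to every 1 of placebo, so equal reaction rates per administration would give twice as many KB103 events. SAP 7.3 already counts doses received. A split by cycle is likewise optional and would rest on about 3 subjects.

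The cost is a wording change and one more column per table, from data already collected. The tables become slightly busier, and event totals may exceed subject counts, which a footnote can explain.

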9.2 Vital Signs

Vital sign measurements include systolic and diastolic blood pressure, pulse, and respiratory rate as well as temperature. Vital signs data is collected at on-site visits.

Descriptive statistics of the absolute and change from baseline to each post-baseline time point values will be provided. Baseline is defined as the value closest to but prior to the initiation of treatment administration.

9.3 Physical/Skin Examination

Physical examinations at screening and subsequent follow-up visits are displayed in tabular format displaying number of subjects examined and number and percentage of subjects with abnormalities by physical examination category. A full physical examination of the body systems is included in the physical/skin examination as follows:

General appearance	Skin
HEENT (Head, Ears, Eyes, Nose, Throat)	Spine/Neck/Thyroid
Respiratory	Cardiovascular
Abdomen	Nervous System
Musculoskeletal	

Subject listings of all physical examination results by body system will be provided. Physical examination results will be coded using MedDRA (version to be delineated in the CSR). Any abnormalities or changes in severity noted during the exam will be provided in a subject listing.

9.4 Laboratory Values

Laboratory data is collected during the study as outlined in the schedule of events ([Appendix 1: Schedule of Events](#)). Reference ranges are used to assess the laboratory data for clinical significance. Abnormal laboratory values which are unexpected or not explained by the subject's clinical condition should be repeated as feasible until confirmed, explained or resolved. Changes from baseline are recorded as an AE if deemed clinically significant by the Investigator or qualified designee.

The following evaluations are conducted:

Serum Chemistry / Metabolic Panel

- | | | | |
|------------------------------|-----------------|--------------------------------|-------------------|
| - Albumin | - AST (SGOT) | - Bilirubin, direct & indirect | - Globulin |
| - Alkaline Phosphatase Total | - Urea Nitrogen | - CO ₂ | - Potassium |
| - Anion Gap | - Calcium | - Creatinine | - Sodium |
| - ALT (SGPT) | - Chloride | - Glucose | - Total Bilirubin |
| | | | - Total Protein |

Hematology / Complete Blood Count with Differential

- | | | | |
|--------------|------------------|--------------------------|--------------------------|
| - WBC | - Platelet Count | - MCHC | - Monocytes, % and abs |
| - Hemoglobin | - MCV RDW | - Neutrophils, % and abs | - Eosinophils, % and abs |
| - Hematocrit | - RBC MCH | - Lymphocytes, % and abs | - Basophils, % and abs |

The absolute and change from baseline laboratory data from the above evaluations will be summarized by treatment and evaluation timepoint. Baseline is defined as the lab value closest to and prior to the first dose of either treatment.

Detailed subject listings of all laboratory data collected during the study will be provided. Laboratory values outside normal limits will be identified in the subject data listings with flags for low (L) and high (H).

Data from the following other laboratory evaluations will be provided in subject listings:

- Urine and Pregnancy Test Results
- HSV Antibody Assay
- Collagen VII Antibody Assay
- Viral Shedding

10 Other Relevant Data Analyses/Summaries

10.1 Protocol Deviations

A listing of all protocol deviations will be provided. Deviations will also be reviewed by the Sponsor and categorized into general categories such as major and minor. Review of protocol deviations will be conducted and finalized prior to analyzing the database. The number of subjects with at least one protocol deviation, the number of subjects with a minor protocol deviation, the number of subjects with a major protocol deviation, and the number of subjects with at least one major deviation in each category will be presented by treatment group for the ITT population. A major deviation is defined as one that potentially affects the efficacy and/or safety analyses.

10.2 Medical/Procedural History

Medical/procedural history is collected during the baseline visit. Medical/procedural history data will be summarized by preferred term and a subject listing will be provided.

10.3 Prior and Concomitant Medications

The prior and concomitant medications will be summarized and listed by treatment. Medications will be coded with WHO and categorized as either prior medications (any medication that was started before the first application of KB103), or concomitant medications (medication continued or newly started on or after the date of first application of KB103). A subject listing also will be provided for all prior and concomitant medications.

11 Appendices

[Appendix 1: Schedule of Events](#)

[Protocol Version 1.0](#)

[Protocol Version 2.2](#)

[Protocol Version 3.1](#)

[Protocol Version 4.0](#)

[Appendix 2: Adverse Event and Prior/Concomitant Medication Date Imputations](#)

11.1 Appendix 1: Schedule of Events

11.1.1 Protocol Version 1.0

Visit	Prescreen	Screen	1	2	3 ¹	4 ²	5				
Week	N/A	-2	0	2	4	6	12				
Day	N/A	-14	0	2	14	28	30	42	84		
Event	Window	N/A	± 2wk	N/A	N/A	± 2d	± 2d	N/A	± 2d	± 5d	LTFU
KB103 Administration ³			X	X	X	X					
Placebo Administration			X	X		X	X				
Phone Screen	X										
ICF / Assent / HIPAA		X									
Inclusion / Exclusion Criteria	X	X	X								
Demographics	X	X									
Medical / Medication History	X	X	X								
Concomitant Medications			X	X	X	X	X	X	X	X	
Adverse Events			X	X	X	X	X	X	X	X	
Physical Exam			X	X						X	
Vital Signs		X	X	X	X	X	X	X	X	X	
Digital Imaging of Wounds ⁴		X	X	X	X	X	X	X	X	X	
Wound Assignment		X									
Pre-dose tattoos		X									
Bacterial Culture										As Needed	
Blood and Urine Tests	Urine Pregnancy Test		X	X							
	Hematology & Chemistry		X	X		X			X	X	
	HIV, Hep B, Hep C Testing		X								
	RCV evaluation		X		X						
	COL7 Antibody Assay ⁵		X		X				X		
	HSV Antibody Assay ⁵			X	X				X		
	Viral shedding assay, urine ⁶		X	X	X	X	X	X	X	X	
	Viral shedding assay, blood ⁶		X	X	X	X	X	X	X	X	
	Genetic Testing	X ⁷									
Day		PS	S	0	2	14	28	30	42	84	
Wound Biopsies	IF for COL7				X	X			X	X	
	qRT-PCR for mRNA and qPCR for viral vector DNA ⁸				X			X			
	IEM for Anchoring Fibrils					X			X	X	
Intact Skin Biopsies	IF for COL7		X ⁷	X ⁷	X	X	X		X	X	
	qRT-PCR for mRNA and qPCR for viral vector DNA ⁸		X ⁷	X ⁷	X	X		X			
	IEM for Anchoring Fibrils		X ⁷	X ⁷	X		X		X	X	

 = Perform the procedure before and after dosing.

 = Optional biopsy. Reference Section 7.2.

¹ If the target wound is closed at Day 28, do not administer KB103 topically.

² If the target wound is closed at Day 28 and then reopens by Day 42, topical KB103 is re-administered at this visit.

³ Topical and intradermal KB103 administration. Skin must be tattooed prior to administration.

⁴ On dosing days, image the KB103 and control wounds both pre- and post-dose.

⁵ May be waived at Day 84 if prior results are negative.

⁶ On dosing days, collect viral shedding samples both pre-dose and 2 hours post-dose.

⁷ Only if needed for diagnosis.

⁸ mRNA and DNA biopsies will minimized to the extent possible (based on previous knowledge) in children

11.1.2 Protocol Version 2.2

Month	1						2	3	3+	
Visit	Screen/BL ¹	1 ²				2	3	4	-	
Day	0	1	2	3	4	5	30	60	90	91-180
Window	n/a				+/-7d		+/-7d	+/-7d	n/a	
Genetic Testing	X									
Bacterial Culture ³	---	--	--	--	--	--	--	--	--	--
Urine Pregnancy Test ³	X	--	--	--	--	--	--	--	--	--
HIV, Hep B, Hep C Testing ³	X	--	--	--	--	--	--	--	--	--
Hematology & Chemistry ⁴	X						X			
COL7 Antibody Assay ⁴	X						X			
HSV Antibody Assay ⁵	X						X			
Wound Assignment	X									
Pre-dose tattoos	X									
Concomitant Medications		X	X	X	X	X	X			
Adverse Events		X	X	X	X	X	X	X		
Viral shedding (skin swab)						X	X	X ⁶		
Physical Exam	X								X	
PRO Assessment	X					X	X	X	X	
Global Wound Assessment	X					X	X	X	X	
Vital Signs	X	X	X	X	X	X	X	X	X	
At-home wound imaging ⁷						X	X	X	X	
On-site wound imaging	X	X	X	X	X	X	X	X	X	
KB103 and Placebo Administration		X	X	X	X	X	X	X	X	
Wound biopsy ⁸						X	X	X		

 = Optional visit for subjects whose wounds have opened.

¹See Section 5.2.2 for a full list of screening procedures

²Diagnostic screening procedures can be performed prior to the visit as indicated below

³Conducted as clinically indicated

⁴After screening, except for Day 30, performed only as clinically indicated to minimize blood draws

⁵May be waived after Day 4 if prior results are negative.

⁶Viral shedding at Day 60 will only be performed if positive at Day 30

⁷Subjects will be instructed to image the target wounds during bandage changes (approximately twice per week).

⁸Biopsies are performed at the discretion of the Investigator and Sponsor. One of the two target wounds should be designated to receive all of the biopsies

11.1.3 Protocol Version 3.1

Visit	1			2	3	4		
Day	0/Screen/BL ¹	1	3	15	30	60 ²	90	91-180 ³
Genetic Testing	X							
Bacterial Culture ⁴	X	X		X	X	X	X	X
Urine Pregnancy Test ³	X	X				X		
HIV, Hep B, Hep C Testing ³	X	X				X		
Hematology & Chemistry ⁵	X				X		X	X
COL7 Antibody Assay ⁴	X				X		X	
HSV Antibody Assay ⁶	X				X		X	
Wound Assignment	X							
Pre-dose tattoos	X							
Concomitant Medications		X	X	X	X	X	X	X
Adverse Events		X	X	X	X	X	X	X
Viral shedding (skin swab)	X	X	X	X	X	X	X	X
Physical Exam	X						X	
PRO Assessment	X				X	X	X	X
Global Wound Assessment	X				X	X	X	X
Vital Signs	X				X	X	X	X
At-home wound imaging ⁷							X	
On-site wound imaging	X	X	X	X	X	X	X	
At-home topical IP administration							X	
On-site topical IP Administration					X	X	X	X
ID KB103 admin to intact skin ⁸					X			
Intact skin biopsy ⁹					X	X	X ⁹	X
Wound biopsy ¹⁰	X				X	X	X	X
X	Optional procedures. Early results may negate the need for ID injection and biopsies to intact skin in later patients.							

¹ Diagnostic screening procedures can be performed prior to the visit as indicated below

² Day 15 and 60 visits are required for patients that receive ID injections to intact skin at Day 1.

³ Follow-up visits after Day 90 are conducted as the subject is able at the discretion of the Investigator

⁴ Conducted as clinically indicated

⁵ After screening/baseline, performed only as clinically indicated to minimize blood draws

⁶ May be waived after the first follow-up visit if prior results are negative.

⁷ Subjects will be instructed to image the target wounds during bandage changes (approximately twice per week). ⁸ Optional ID administration for subjects at least 13 years old. Performed at the discretion of the Investigator. Early results may negate the need for ID injection and biopsies to intact skin in later patients.

⁹ Two intact skin locations will be biopsied on Day 30

¹⁰ Biopsies are performed at the discretion of the Investigator and Sponsor.

